### 2. INTRODUCTION

Cardiac surgery requiring cardiopulmonary bypass (CPB) has been routine in clinical practice for over 50 years and numerous technological advancements have taken place over this time. This procedure has been lifesaving, by allowing many complex cardiac surgical procedures to take place safely. However, despite advances in perfusion, anesthetic and surgical techniques, CPB still frequently evokes inflammatory and hemolytic reactions that may lead to worsening of renal function and postoperative morbidity. The incidence of renal damage has been estimated between 10-25% with little improvement despite extensive investigation. Furthermore this rate is higher for patients with significant co-morbidities such as diabetes or congestive heart failure.

The pathogenesis of cardiovascular surgery associated renal injury is multifactorial, including CPB associated intravascular hemolysis (resulting in the generation of pfHb), exposure of blood to CPB surfaces during surgery with initiation of the early phase inflammatory response via contact activation and an acute rise in inflammatory mediators during the procedure including: complement activation, the coagulation system, leukocytes, cytokines, chemokines, and adhesion molecules. Multiple factors including temperature variation and oxygenation may further escalate the immune response. This combination of processes was described as the Systemic Inflammatory Response Syndrome (SIRS) and is associated with frequent complications of renal failure.

Mitigation of the deleterious effects of renal injury therefore requires a multimodal strategy aimed at decreasing circulating factors likely to exacerbate tissue injury during the period of heightened risk, i.e., during CPB. Two well characterized etiologies of worsening renal function are the generation of pfHb and activated complement during CPB.

Circulating levels of pfHb are normally low; however, hemolysis increases dramatically during CPB surgery, resulting in increased pfHb. The extent of hemolysis during CPB surgery is directly correlated with both the length of the CPB procedure (> 3 hours) and the complexity of cardiac surgery. Red blood cells (RBCs) can hemolyze during CPB due to factors such as negative pressure cardiotomy suction, blood material interactions, increases in foreign surface to-blood volume ratios, shear stress due to high flow rates through artificial blood circuits, and others.

The mechanisms whereby hemoglobin is thought to induce renal injury or dysfunction include (a) tubular obstruction caused by heme protein precipitation, (b) ischemic injury resulting from increased renal vascular resistance and vasoconstriction, and (c) heme iron-driven oxidative injury. By overwhelming the macrophages associated uptake of Haptoglobin-Hb complexes high levels of pfHb may lead to inflammation and endothelial, tissue, and organ injury. Hemoglobin first reacts with endogenous compounds to form oxygen radicals that induce prooxidant damage. This damage is known to promote a pro-inflammatory cascade and cellular interactions through pathways involving activation, generation, or expression of thrombin, complement, neutrophils, cell-adhesion molecules, mast cells, and TNF- $\alpha$  5. These mediators

have been shown to be associated with the development of postoperative SIRS, and major postoperative complications.

Hemolysis, resulting in release of free hemoglobin (pfHb), has been directly correlated with induction of kidney injury. In one study reported in the literature, peak pfHb levels  $\geq$  64.5 mg/dL held a significant diagnostic value for the prediction of acute kidney injury (AKI). The complications of AKI may require increased length of stay and ICU time, prolonged mechanical ventilation, increased risk of nosocomial infections, or may increase the risk for systemic inflammatory response syndrome (SIRS) and potential progression to organ failure. Kubota et al. noted a protective effect of haptoglobin infusion intraoperatively to reduce the incidence of post-operative AKI, indicating that the uptake of Haptoglobin-Hb complex by macrophages may be protective against the tissue injury associated with pfHb. Because of this, the removal of pfHb during CPB has the potential to significantly reduce the risk of hemolysis-induced organ injury.

Activation of the complement alternative pathway also occurs during CPB and examination of clinical samples and preclinical models has shown that activation of the complement system is a critical cause of acute kidney injury. Eculizumab, an anti-C5 monoclonal antibody inducing terminal complement blockade, showed reduced complement activation, inflammation, endothelial damage, thrombosis, and renal injury markers in an exploratory study of atypical hemolytic uremic syndrome (aHUS). Precedent for complement inhibition was also established using soluble human complement receptor type 1 (sCR1) and heparin bound CPB circuits.

By directly causing tissue injury in the post-operative SIRS response, and through adverse physiologic changes, pfHb is thought to be a significant contributor in the development of multiple organ failure (MOF) in many patients following cardiac surgery. These complications may require increased length of stay and ICU time, prolonged mechanical ventilation, increased risk of nosocomial infections, or may increase the risk for systemic inflammatory response syndrome (SIRS) and potential progression to organ failure. The renal toxicity associated with the generation by cardiac surgery of both pfHb and inflammatory mediators (activated compliment cascade and inflammatory cytokines) suggests that an intra-operative reduction of these elements may reduce the potential for post-operative complications, improve clinical outcomes and reduce the risk of renal injury.

Despite ongoing efforts to mitigate the effects of CV surgery, only limited progress has been made in altering the prevalence of surgically associated renal injury as assessed by the clinically accepted definitions of acute kidney injury (AKI) and in long term morbidity associated with decreased renal function. A potential reason may be the failure to prevent the loss of renal functional reserve occurring below the threshold of creatinine elevation that defines AKI. Ishani et al linked the magnitude of sCr increase post cardiac surgery to increasing rates of chronic kidney damage (CKD), progression of kidney disease and death. Similarly, even minimal increases in sCr were associated with adverse long-term outcomes Duque-Sosa and Lassnigg, et al observed that even minimal (0.1 mg/dl) increases in sCr, in the immediate postoperative period, were associated

with significantly increased mortality, providing an independent risk factor in predicting outcome after cardiac surgery.

### 2.1 Summary of Previous Clinical Experience Informing Study Design:

CytoSorbents conducted REFRESH I, a prospective, randomized, controlled safety trial enrolling a small heterogeneous population, at eight major U.S. cardiac surgery centers to evaluate the safety and feasibility of CytoSorb®, a blood purification technology designed as an adjunctive therapy to remove inflammatory mediators (i.e., pfHb, activated complement and cytokines) in high risk cardiac surgery patients aged 18-80 years of age, where cardiopulmonary bypass (CPB) was expected to exceed 3 hours. Subject assessments were performed until subjects were discharged from the ICU. Subjects were monitored for AEs through 30 days after the procedure.

This trial achieved the primary safety endpoint of the study with a favorable adjudication of all serious adverse events. There were no significant differences in the rates of adverse events (AEs) or serious adverse events (SAEs) between the two groups, including 30-day mortality, and no unanticipated adverse device effects (UADEs) were reported. Three subjects (1 Control; 2 Treated) died of AEs that were considered by the Independent Physician Adjudicator to be not related to the device. Most AEs were related to the pre-existing conditions or to surgical procedures. AEs specifically related to the investigational device were infrequent (i.e., involving 2 [8.7%] subjects in the Treated arm) and in both instances the subjects recovered without sequelae.

A detailed description of the REFRESH I study results along with subsequent safety analyses of REFRESH I data; safety information derived from clinical applications other than CPB; and supporting preclinical assessments may be found in the Investigator Brochure. The investigator should read and understand the Investigator Brochure and use it in conjunction with this protocol in the evaluation of risk and benefit for patients being considered for enrollment into this study.

### 2.2 REFRESH II Study design:

The REFRESH II study is designed to assess the intraoperative use of the CytoSorb® device in patients with an increased risk of acute renal failure following open heart surgery to decrease the circulating presence of nephrotoxic agents (such as pfHb, cytokines, and activated compliment during CPB) in conjunction with standard of care treatment. The study aims to determine whether the use of the CytoSorb® device can decrease the incidence or severity of AKI in the 48 hours immediately following surgery. This will be evaluated in a patient population that has been enriched for increased risk of cardiac surgery associated AKI and for procedures associated with a higher risk for pfHb generation.

In this study, creatinine and urine output collection will be used to identify acute kidney injury (AKI) as defined by the KDIGO clinical practice guidelines. This identification will be augmented through the use of additional indicators of renal damage and dysfunction, including assays for urinary TIMP2 and IGFBP-7 and serum elevations in HMGB1 and Cystatin C.

The CytoSorb® device that will be utilized in this randomized and blinded trial is based on size adsorption filtration. Each CytoSorb® adsorber cartridge contains micro-porous, polystyrene bead technology. Earlier in vitro and in vivo studies have shown this to correlate with the removal of endogenous mediators of inflammation and pfHb. This product, approved under a CE mark in Europe and other countries has been used in over 25,000 critical care cases, including about 6,000 cardiac surgery cases. It is believed that the removal of these renal-toxic substances from patient blood during surgery will lead to an overall reduction in kidney dysfunction among the patients who assigned to the treatment group relative to those who will be on standard of care alone.

### 3. INVESTIGATIONAL DEVICE DESCRIPTION

### 3.1 Investigational Device Description

CytoSorb® is a sorbent-filled hemoperfusion cartridge that is designed to reduce plasma free hemoglobin and other inflammatory mediators from blood that are generated during cardiopulmonary bypass in cardiac surgery. The device is placed into a parallel bypass circuit (between the oxygenator and the venous reservoir) in a standard heart-lung machine.

CytoSorb® consists of a cylinder and end-cap assembly filled with biocompatible porous polymer beads (**Figure 1**). At either end of the cylinder, a fine mesh screen is placed to retain the polymer beads within the device. Each end-cap has a standard dialysis connector, which is compatible with standard dialysis tubing. The polymer beads are composed of a divinylbenzene/polyvinyl pyrrolidone co-polymer, where each bead has hundreds of thousands of tightly controlled pores and channels that are generated via suspension polymerization. These pores and channels, in turn, enable the porous polymer beads to remove middle molecular weight substances based on pore capture (size) and surface adsorption.

The CytoSorb® device is designed for use in an extracorporeal circuit. The device can be connected on a standard heart-lung machine in a parallel configuration with the CPB circuit. The target flow rate through the device is intended to be approximately 300-400 mL/min which is about 10-20% of a typical flow rate encountered in CPB. In this study, two parallel CytoSorb® cartridges will be attached to the bypass circuit, and they are connected between the oxygenator and cardiotomy reservoir as shown in the **Figure 2** below and separate from the main blood flow to the patient. These devices will be used as such; for the first 90 minutes of CPB, blood will be directed through the first of the two devices. If and when CPB continues for more than 90 minutes, the second CytoSorb® device will then be opened to the perfusion circuit. Blood flow through the CytoSorb® circuit is controlled via an adjustable roller clamp distal to the cartridges and monitored via ultrasonic flow detection (a Transonic, or equivalent) flow monitor will be supplied) to maintain a target blood flow of ~800 mL/min with both devices, or ~400 mL/min with the single device. A minimum flow of ~300 ml/min through the single device, or ~600 ml/min through the complete circuit (both devices) is acceptable. Once the hemoperfusion session is

complete, remaining blood in the circuit goes back to the patient, if appropriate per hospital protocol.

In addition to the CytoSorb® device, two off-the-shelf disposable connector and tubing sets supplied from Molded Products based on their commercial Y-Blood line set CYT800-C (both covered by 510k K003712) will be used to connect the CytoSorb® devices to the oxygenator and venous reservoir. A standard roller clamp and disposable hemostats will also be provided.

Figure 1: CytoSorb® Device

Figure 2: CytoSorb® 300 mL Device on CPB Circuit

### 3.2 Investigational Device Identification

The CytoSorb® 300mL device will be used in this study. It is anticipated that two CytoSorb® devices (in parallel) will be used for each subject randomized to the treatment arm.

### 3.3 Investigational Device Accountability

Each CytoSorb® device will be assigned lot numbers and/or unique serial numbers. Access to investigational devices shall be controlled and the investigational devices shall be used only in the clinical investigation and according to the clinical investigation plan. The sponsor will keep records to document the physical location of all investigational devices from shipment of investigational devices to the investigation sites until return or disposal. The Principal Investigator or an authorized designee shall keep records documenting the receipt, use, return and/or disposal of the investigational devices, which shall include:

- Date of receipt;
- Identification of each investigational device (lot number/serial number);
- Expiry date;
- Date of use;
- Study identification;
- Date on which the investigational device was returned, if applicable, and;
- Date of return of unused, expired or malfunctioning Investigational Intended Use/Current Indication for Use

### **3.4** The intended use of the investigational device(s).

The proposed investigative use of CytoSorb® device is in an extracorporeal circuit for the removal of free hemoglobin as an adjunct to the standard of care in subjects undergoing cardiac surgery requiring CPB and will only be used as specified by this clinical protocol.

### 3.5 Investigational Device Procedure(s)/Training

The CytoSorb® device is designed for use in a standard heart-lung machine CPB circuit with an arterial pump. In this study, as described in the Instructions for Use (IFU), up-to two CytoSorb® cartridges in a parallel configuration will be in a bypass circuit connected between the oxygenator and cardiotomy reservoir as shown in **Figure 2**, and separate from the main blood flow to the subject. Blood flow through this circuit is controlled via an adjustable roller clamp distal to the cartridges and monitored via ultrasonic flow detection to maintain flow. A minimum blood flow of ~ 300 ml through the single device, or ~ 600 ml through the paired devices together is acceptable.

The circuit containing the CytoSorb® devices will be connected prior to the start of the procedure. Blood flow through the first CytoSorb® device will commence when subject goes on CPB. Flow through the second CytoSorb® device will commence at 90 minutes from the start of CPB (at this time both CytoSorb® devices will have blood flowing through them). Use of the CytoSorb® devices is stopped at the end of CPB. Once the CPB procedure is complete the hemoperfusion session will be ended, the circuit is flushed with saline, with the return of blood in the circuit back to the subject, per the hospital protocol.

CytoSorb® device training for the device users involved in this study will occur prior to CytoSorb® device use and will be documented in a training log.

### 3.6 Blinding

Blinding to treatment assignment, as implemented in this study will apply only to select study personnel and for specific durations. Blinding of the surgical staff to treatment assignment is implemented in this study starting at the point of randomization and extending through the duration of the entire study. This blinding is implemented to minimize bias in surgical care decisions that may be introduced by knowledge of treatment assignment. The potential for introduction of bias is most relevant during the surgical procedure where knowledge of treatment assignment and prior clinical experience with the investigational device may impact clinical decisions such as frequency of platelet or whole blood infusion and assessment of adverse events that occur during surgery by medical staff responsible for administering these treatments.

To minimize bias both subjects and designated site study personnel (e.g. Surgeon, Anesthesiologist, OR staff) involved in OR activities will be blinded to the treatment assignment. The study coordinator may remain unblinded, however extreme caution should be exercised by the study coordinator to prevent inadvertently revealing treatment assignment to individuals making clinical decisions on subject care.

The unblinded team at the site (Perfusionist and study coordinator) will be supplied with a barrier to separate the perfusion area from the surgical staff view. A Field Clinical Engineer (FCE), as designated by the Sponsor, may be present to assist with set up of the blind and provide guidance during the procedure.

### 3.6.1 Maintaining the Study Blind

The following describes the measures being taken to maintain the study blind.

- a) **Subjects:** Subjects will not be told their randomization assignment by any site study personnel involved in the trial and will receive the same care throughout the trial.
- b) **Randomization Assignment:** Each site will randomize subjects using the electronic data base. After the appropriate information is entered into the electronic case report form (eCRF), the randomization function will be activated, and the assignment made (Standard of Care or Standard of Care with CytoSorb® Device). This randomization process is performed by the unblinded team within 5 business day prior to the procedure, including the day of the procedure.
- c) Site Study Personnel: There are two designated teams at each site:
  - Blinded: These individuals remain blinded from the point of randomization through the duration of the study, inclusive of all subjects enrolled at the site.
    - Surgical team
    - Anesthesiologist
  - Unblinded: These individuals will be aware of treatment assignment and will refrain from revealing it to any other study staff for the duration of the study, inclusive of all subjects enrolled at the site.
    - Perfusionist
    - Study Coordinator
    - o FCE

The **Blinded Team** is responsible for administering all pre-, intra- and post-procedure subject testing and care as designated by the protocol.

The **Unblinded Team** is responsible for those activities and documentation related to the procedure, including the selection of the device (sham or CytoSorb®) used at time of procedure, and recording the procedure and device study data in the eCRFs and device accountability log. The Sponsor will work with each individual site to determine the documentation needed in the subjects' medical records (e.g. procedure notes) to protect the study blind. The Study Coordinator on this team remains unblinded to the subject treatment assignment and is particularly responsible for:

1. Obtaining randomization code from EDC system within 5 business days prior to procedure including day of procedure

- 2. Ensuring appropriate device cartridges are available and in OR suite on procedure day
- 3. Completing Device Accountability Log
- 4. EDC entry for all data pertaining to treatment assignment and procedure information
- 5. EDC entry for any AEs associated with the use of the device or procedure that are assessed and any additional EDC entry
- 6. Scheduling routine follow-up care/visits for all study subjects
- 7. Performing follow-up visits

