#### 6.2 Study Design

This will be a prospective, multi-center, randomized, pivotal, double-blinded clinical study. Subjects will be randomized in a 1:1 ratio to either standard of care (SOC) alone or standard of care and treatment with the CytoSorb® device, with or without HCA. Number of patients with and without HCA will be assessed in the interim analysis

Interim analyses will be carried out for potential (NON-BINDING) early stopping for an efficacy or futility conclusion.

An option to increase sample size (SSR, i.e., Sample Size Re-estimation) will be considered. SSR is based on the second interim analysis results using conditional probability (CP) to estimate the sample size necessary to boost the CP to 88%, assuming the observed response proportions are the TRUE underlying proportions.

To assure proper startup of the sites we will employ a roll in approach for up to the first two enrolled subjects from each site for training. All subjects enrolled as roll-in cases are treated with CytoSorb® device and are followed per protocol. The roll-in cases will be analyzed for safety as outlined in Section 11.1.1.

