### 8.7 Day 30 Post-Cardiac Surgery

The subjects will be contacted via telephone at 30 days post-cardiac surgery for assessment of the following since hospital discharge:

- Blood product transfusions
- Adverse events

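### The Day 30 safety call falls to the unblinded study coordinator, so post-discharge adverse events are elicited with knowledge of the arm in a trial labelled double-blinded

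*Protocol*

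**What the plan says.** - **Label.** Protocol Section 6.2: "This will be a prospective, multi-center, randomized, pivotal, double-blinded clinical study". The protocol synopsis and SAP Section 4 use the same label.
- **Scope of the blind.** Protocol Section 3.6: "Blinding to treatment assignment, as implemented in this study will apply only to select study personnel and for specific durations".
- **Coordinator's status.** Section 3.6 is permissive: "The study coordinator may remain unblinded". Section 3.6.1 is definite: "The Study Coordinator on this team remains unblinded to the subject treatment assignment and is particularly responsible for" a numbered list of tasks.
- **Coordinator's tasks (Section 3.6.1).** Item 5 is "EDC entry for any AEs associated with the use of the device or procedure that are assessed", together with any other data entry. Item 6 is scheduling of follow-up. Item 7 is "Performing follow-up visits".
- **Blinded team's task (Section 3.6.1).** This team, listed as the surgical team and the anesthesiologist, is "responsible for administering all pre-, intra- and post-procedure subject testing and care as designated by the protocol".
- **Contact after discharge.** Section 8.7: "The subjects will be contacted via telephone at 30 days post-cardiac surgery for assessment of the following since hospital discharge". Two items follow: blood product transfusions and adverse events.
- **End of the blind.** Section 3.6.2 plans to unblind subjects and site personnel only once the 30-day assessments are complete and the data verified.
- **Safety endpoints.** The primary one is device-related adverse events over the study period (Section 6.3.1). A secondary one is procedure-related adverse events through 30 days (Section 6.3.3). SAP Section 6.8.1 attaches no formal hypothesis to the primary safety endpoint.

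**The concern.** Adverse events after discharge are largely found by asking. How a question is put, how far a vague answer is pursued and what is written down are all discretionary. If the caller knows which patients had the device, that discretion can operate differently in the two arms. More events could be recorded in the device arm through extra vigilance, or fewer through confidence in the device.

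At stake is the comparability between arms of post-discharge adverse event rates. The most exposed result is the secondary endpoint of procedure-related events through 30 days, and within it the non-serious events. Section 3.6.2 shows that the site blind is meant to last through the 30-day assessments, yet the one scheduled assessment after discharge is given to a role that is never blind.

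**Working it through.** The plan gives no figure on this point, so the check is a reading of the sections against each other.

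**Step 1: who makes the call?** Section 3.6.1 item 7 gives follow-up visits to the coordinator. After discharge the schedule has one follow-up contact, the 30-day contact in Table 3, which Section 8.7 describes as a telephone call. Section 6.4.4 also refers to it as a call. So the Day 30 call falls to the coordinator.

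**Step 2: does the caller know the arm?** Yes under Section 3.6.1. Section 3.6 only permits this. The two sections differ, and neither requires a blinded caller.

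**Step 3: what does the call collect?** Only adverse events and transfusions since discharge (Section 8.7). Creatinine and urine output for the 48-hour AKI endpoint are collected in hospital (Sections 8.1 and 8.2), so that endpoint is outside this point.

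**Step 4: is the enquiry standardised or masked elsewhere?** Sections 8.7, 8.8.1 and 8.9.1 describe no scripted question list. Section 8.8.1 has the Investigator or a designee determine occurrence and give an opinion on device relationship, and Section 8.9.1 has the Investigator or designee complete the form. None of these sections says that this person must be blind to arm. SAP Section 4.3 only refers back to protocol Section 3.6.

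**Step 5: does a later check repair it?** The Clinical Events Committee (Section 9.1) reviews reported device- or procedure-related serious events within 30 days. An event that was never elicited, or that is not serious, does not reach it. The protocol does not say whether the committee is blinded.

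**Step 6: can a size be given?** Not from the documents. The mechanism can be written as

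spurious difference = p × (r1 − r2),

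where p is the true share of patients with a post-discharge event (taken as equal in both arms) and r1 and r2 are the recording rates by arm. All three are unknown. With p assumed at 0.20 to 0.30, r1 at 0.90 and r2 at 0.70 to 0.80:

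- p = 0.20: 0.20 × 0.10 = 2 points, up to 0.20 × 0.20 = 4 points
- p = 0.30: 0.30 × 0.10 = 3 points, up to 0.30 × 0.20 = 6 points

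This shows only how an assumed recording gap carries through to the rates. It is not an estimate for this trial, and the sign could go either way.

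**The case against.** Much of the case on the other side stands, and it limits the point.

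- **Causality.** A reader might infer that the coordinator decides which events count and whether they are device-related. The text does not support that. Item 5 is data entry of events already assessed. Sections 8.8.1 and 8.9.1 place occurrence, relatedness and reporting with the Investigator or a designee. What remains is arm-aware elicitation and recording.
- **Sole source.** A reader might infer that the call is the only source of post-discharge events. It is the only scheduled contact. Table 3 collects adverse events as needed until study exit, and Section 8.9.1 requires serious events to be reported within 24 hours of site knowledge, however they come to light.
- **Share of the window.** With discharge assumed at Day 5, 7 or 10, (30 − 5)/30 = 83%, (30 − 7)/30 = 77% and (30 − 10)/30 = 67% of the 30 days follow discharge. A reader might take this as the share of the safety evidence affected. It is a share of calendar days, not of events. The device runs only during bypass, and many of the device effects listed in Section 8.8.3 (leaks, clotting in the device, falls in platelets, white cells and albumin) would be expected in hospital. The primary safety endpoint is therefore less exposed than procedure-related events through 30 days.
- **Contradiction within Section 3.6.1.** A telephone enquiry is arguably neither testing nor care, so the two teams' duties can coexist. This is loose wording that needs reconciling.
- **Rationale in Section 3.6.** It speaks of events during surgery, so it cannot be read as a promise of masked assessment after discharge.
- **Openness and safeguards.** Section 3.6 states that the blind is partial, subjects are to be kept blind, and the Clinical Events Committee covers related serious events. A script might exist in the study manual or case report forms, which are not among the documents.

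None of this removes the central fact: followed as written, the plan gives the Day 30 enquiry to someone who knows the arm.

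**Conclusion.** The point holds in a limited form. The Day 30 call, the only scheduled contact after discharge, is assigned to an unblinded coordinator in a trial labelled double-blinded. This opens elicitation and recording of post-discharge adverse events to differential ascertainment, chiefly procedure-related events through 30 days and non-serious events outside the Clinical Events Committee's remit.

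Size and direction are unknown. No test or error rate for the primary safety endpoint is affected, because SAP Section 6.8.1 makes it descriptive, although descriptive rates by arm can still be distorted. The conclusion assumes that sites followed item 7 as written and that no document outside those reviewed prescribes a masked or scripted enquiry. It merits correction because the remedy is cheap and specific, not because a bias has been shown.

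**What to change.** 1. Amend Section 3.6.1 item 7 so that the adverse event and transfusion enquiry at Day 30 is made by an existing blinded member of the site team. Where that cannot be arranged, require at minimum one fixed script, read identically in both arms.
2. State in Section 8.8.1 that the Investigator who determines occurrence and relatedness does so from the recorded narrative and blind to arm.
3. Reconcile Sections 3.6 and 3.6.1 on whether the coordinator may be, or is, unblinded, and on where the blinded team's post-procedure duties end and the coordinator's begin.
4. SAP Section 4.1 reports that the study stopped early with 151 subjects enrolled, so an amendment cannot repair calls already made. For those, the final report should state who elicited Day 30 adverse events and qualify the double-blinded label for post-discharge safety data.

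**Cost.** A change of delegation, a short script, and one brief call per patient moved to blinded staff. Because Section 3.6.1 lists only the surgical team and the anesthesiologist as blinded, this is a real though small scheduling burden at each site, which is why the script is offered as the minimum. No added visits, procedures or sample size are needed.
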